9.0 STUDY OBJECTIVES

The objectives of this study are to:

1. Evaluate the therapeutic equivalence of the Test formulation, Ivermectin Lotion 0.5% (Actavis Laboratories UT, Inc.) to the Reference product, SKLICE® (ivermectin) Lotion, 0.5% (Arbor Pharmaceuticals, LLC) in the treatment of active head lice infestation.
2. Demonstrate the superiority of the Test and Reference (active) treatments over Placebo treatment in patients with active head lice infestation.
3. Compare the safety of Test, Reference and Placebo treatments in patients with active head lice infestation.

10.0 INVESTIGATIONAL PLAN

[figure not shown]
10.1 Study Design and Plan Description

This randomized, double-blind, placebo-controlled, parallel-design, multiple-site clinical study has been designed to evaluate the efficacy and safety of a generic Ivermectin Lotion 0.5% (Actavis Laboratories UT, Inc.) compared to the Food and Drug Administration (FDA) Reference Listed Drug (RLD) SKLICE® (ivermectin) Lotion, 0.5% (Arbor Pharmaceuticals, LLC) in patients with active head lice infestation. Additionally, both the Test and Reference (i.e., the RLD) treatments will be tested for superiority to a Placebo.

Before any study-specific procedures are performed, all patients will read and sign the IRB-approved informed consent form (ICF). In addition, patients who are considered minors in the state the study is being conducted (< 18 years of age in most states), must have a signed parental/guardian ICF, indicating approval to participate, as well as a signed assent to participate form, as appropriate. Patients 11-17 years of age will read and sign an IRB-approved assent form and patients 6-10 years of age will provide verbal assent. Patients 6 months-5 years of age will be exempt from providing assent based on the child's comprehension and cognitive skills.

Males and females, 6 months of age and older with an active head lice infestation will be randomized [REDACTED] to one of the three study products as follows:

- **Test:** Ivermectin Lotion, 0.5% (Actavis Laboratories UT, Inc.)
- **Reference:** SKLICE® (ivermectin) Lotion, 0.5% (Arbor Pharmaceuticals, LLC)
- **Placebo:** Placebo (vehicle) lotion (Actavis Laboratories UT, Inc.)

Patients, infested household members, and/or caregivers will be instructed to administer a single application of the study product to the hair on the day of or the day after enrollment into the study,

CONFIDENTIAL PROTOCOL

A Randomized, Double-Blind, Placebo-Controlled, Parallel-Design, Multiple-Site Clinical Study to Evaluate the Therapeutic Equivalence and Safety of Ivermectin Lotion 0.5% (Actavis Laboratories UT, Inc.) to SKLICE® (ivermectin) Lotion, 0.5% (Arbor Pharmaceuticals, LLC) in the Treatment of Human Head Lice Infestation

leave the study product on the hair and scalp for 10 minutes, and then rinse off with warm water. Patients and infested household members will be instructed to apply the study product at home. The day of dosing will be considered Day 1.

Patients will attend the following four scheduled clinics visits:

- Visit 1 (Day -1 to 1): Screening/Baseline
- Visit 2 (Day 2): Interim Visit
- Visit 3 (Day 8 ± 2): Interim Visit
- Visit 4 (Day 15 ± 2): End of Study

At Visit 2 (Day 2), [REDACTED] enrolled [REDACTED] will return the study product to the clinic. Visit 2 must occur the day after dosing. [REDACTED]

[REDACTED]. At Visits 2, 3, and 4, patients will be examined for the presence of live head lice (i.e., live adults and/or nymphs). Louse examination should be conducted for 15 minutes or longer, unless any live lice are detected in less time. Duration of examination should be recorded. [REDACTED]

[REDACTED] Unscheduled visits will be allowed as deemed necessary by the Investigator or Sponsor to ensure patient safety or to perform other study-related procedures.

At Visit 2, patients will be questioned about any ocular discomfort associated with the study product. Also at Visits 2, 3, and 4, patients will be questioned about any adverse events (AEs), application site reactions (Appendix A), and any new concomitant medication use.

Definitions

- [REDACTED]
- [REDACTED]
- Non-index patient: Any household member who has agreed to participate in the study but is not the youngest member of the household.
- Index patient: The youngest household member who is randomized into the study.

Therapeutic equivalence will be assessed by evaluating the proportion of index patients in each treatment group who are considered a Treatment Success on Day 15 ± 2. Treatment Success is defined as the absence of live lice. The proportion of all patients (i.e., index + non-index) who are considered a Treatment Success on Day 15 ± 2 will be evaluated as a secondary endpoint. The analysis of superiority will compare both active treatment groups to the Placebo group for the same primary and secondary endpoints.

CONFIDENTIAL PROTOCOL

A Randomized, Double-Blind, Placebo-Controlled, Parallel-Design, Multiple-Site Clinical Study to Evaluate the Therapeutic Equivalence and Safety of Ivermectin Lotion 0.5% (Actavis Laboratories UT, Inc.) to SKLICE® (ivermectin) Lotion, 0.5% (Arbor Pharmaceuticals, LLC) in the Treatment of Human Head Lice Infestation

10.2 Selection of Study Design

This protocol is based on procedures and results from studies conducted as part of the New Drug Application (NDA) # 202-736 for SKLICE® (ivermectin) Lotion, 0.5%, recommendations from the FDA industry guidance for the development of topical head lice drugs, and recommendations from the FDA guidances on malathion lotion, 0.5% and spinosad topical suspension, 0.9%, which are products that have a similar indication and usage for treatment of head lice infestation.^{11,12,15,16}

10.3 Selection of Study Population

10.3.1 Inclusion Criteria

1. Signed Institutional Review Board (IRB)-approved ICF that meets all criteria of current FDA regulations. For patients who are considered minors in the state the study is being conducted (< 18 years in most states), the parent or legal guardian should sign the consent form and the child will be required to sign a patient “assent” form, as appropriate. Patient 11-17 years of age will read and sign an IRB-approved assent form and patients 6-10 years of age will provide verbal assent. Patients 6 months-5 years of age will be exempt from providing assent based on the child’s comprehension and cognitive skills.
2. The patient and/or the patient’s parent (legal guardian) is willing to apply the study product as directed, comply with study instructions and commit to all follow-up visits for the duration of the study.
3. Male or non-pregnant, non-lactating female, 6 months of age or older.
4. Females of childbearing potential must not be pregnant or lactating at Visit 1 (as confirmed by a negative urine pregnancy test with a sensitivity of less than 50 mIU/mL or equivalent units of human chorionic gonadotropin). Women of childbearing potential must agree to the use of a reliable method of contraception (e.g., total abstinence, intrauterine device, a double-barrier method, oral, transdermal, injected, or implanted non-hormonal or hormonal contraceptive) throughout the study. Female patients using hormonal contraceptives should have been on the same product/dosing regimen for at least 28 days before Visit 1 and should not change this regimen during the study. A sterile sexual partner is not considered an adequate form of birth control.
5. Index patients (i.e., the youngest household member) must have an active head lice infestation, defined as ≥ 3 live lice (i.e., live adults and/or nymphs), at Visit 1.
6. Household members participating in the study must have at least one live louse (i.e., live adults and/or nymphs) at Visit 1.
7. All members of the household must be present for examination. Any male head of household who is unable to attend Visit 1 may be assessed by a second household member as being lice free.

10.3.2 Exclusion Criteria

1. Females who are pregnant, lactating or planning to become pregnant during the study period.

CONFIDENTIAL PROTOCOL

A Randomized, Double-Blind, Placebo-Controlled, Parallel-Design, Multiple-Site Clinical Study to Evaluate the Therapeutic Equivalence and Safety of Ivermectin Lotion 0.5% (Actavis Laboratories UT, Inc.) to SKLICE® (ivermectin) Lotion, 0.5% (Arbor Pharmaceuticals, LLC) in the Treatment of Human Head Lice Infestation

2. Patients who do not have a known household affiliation with their household members (i.e., do not stay in one household consistently, sleeping at one place several nights and then at another place or location). Household is defined as living in a shared area or space (for example the same house or apartment unit).
3. Any infested member of the household is unable or unwilling to be treated with the study product. This includes male heads of household who do not attend Visit 1 but report infestation with lice.
4. More than three members of the household infested with lice.
5. Presence of visible skin/scalp condition(s) or open wounds at the application site that are not attributable to head lice infestation and that in the opinion of the Investigator will interfere with safety and/or efficacy evaluations.
6. Presence of eczema or atopic dermatitis at the application site.
7. Use of any prescription, OTC, or home remedies for the treatment of head lice within 7 days before Visit 1.
8. Use of pediculicides within 4 weeks before Visit 1.
9. Use of systemic anti-parasitic agents within 4 weeks before Visit 1.
10. Patients with very short (shaved) hair or who are planning to shave head during the study.
11. Use of any hair dye, bleaches, hair straightening or permanent wave solution on the hair within 14 days before Visit 1.
12. History of allergy or sensitivity to pediculicides or hair care products.
13. History of any drug hypersensitivity or intolerance that, in the opinion of the Investigator, would compromise the safety of the patient or results of the study.
14. Significant history or current acute or chronic infectious disease, system disorder, Netherton's Syndrome, organ disorder (e.g., hepatic or renal impairment) or insufficiency, immunosuppression (from medical treatment or disease), organ transplant, uncontrolled diabetes, uncontrolled hypertension, current ocular condition, or other medical condition that, in the Investigator's opinion, would place the study patient at undue risk by participating in the study.
15. Patients or non-infested household members who would act as the primary caregiver who are of intellectually competent age but unable to understand the protocol requirements, instructions, and study-related restrictions, the nature, scope, and possible consequences of the clinical study.
16. Receipt of any drug as part of a research study within 30 days before Visit 1.
17. The patient is a member of the investigational study staff or a member of the family of the investigational study staff.

CONFIDENTIAL PROTOCOL

A Randomized, Double-Blind, Placebo-Controlled, Parallel-Design, Multiple-Site Clinical Study to Evaluate the Therapeutic Equivalence and Safety of Ivermectin Lotion 0.5% (Actavis Laboratories UT, Inc.) to SKLICE® (ivermectin) Lotion, 0.5% (Arbor Pharmaceuticals, LLC) in the Treatment of Human Head Lice Infestation

18. Previous participation in this study.

10.3.3 Restrictions During the Study

The following concomitant medications, products or procedures will not be allowed while enrolled in the study:

- Any prescription, OTC, home remedy, or mechanical/manual methods (e.g., nit combing) for the treatment of head lice. This includes any medicated shampoos specifically used in the treatment of head lice.
- Pediculicides.
- Hair dye, bleaches, hair straightening or permanent wave solution on the hair.
- Topical or systemic anti-parasitic agents.

Patients will be instructed to avoid occlusion of the scalp with any agent (e.g., petroleum) and sleeping at different locations. Patients should not shave their head until after study completion.

Patients will be questioned about all prescription and OTC concomitant medication use (including vitamins or nutritional supplements) at each study visit. All concomitant medications will be recorded in the patient's source documents. Any patient who violates any of the listed restrictions may be dropped from continued participation in the study by the Investigators.

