10.3.4 Removal of Patients From the Study

Patients will be advised that they are free to withdraw from the study at any time. If necessary, the Investigator may withdraw a patient from the study to protect the health of that patient. In case of early termination the Investigator will fully document the reason for early termination. The clinical report will include all reasons for early withdrawals. Reasons for removal may include the following:

- Patient withdrew consent.
- Significant AE that led the Investigator or patient to withdraw for safety reasons.
- Non-compliance with protocol requirements (e.g., use of restricted medication, not following dosing procedures, failure to make scheduled study visits in a timely fashion).
- Presence of live lice at any post-treatment visit.
- Participant enrolls in another clinical trial during the study, or is found to have previously enrolled in this clinical trial.

If a randomized patient terminates from the study early, all efforts will be made to complete the End of Study procedures. Patients who withdraw or are removed from the study will not be replaced.

CONFIDENTIAL PROTOCOL

A Randomized, Double-Blind, Placebo-Controlled, Parallel-Design, Multiple-Site Clinical Study to Evaluate the Therapeutic Equivalence and Safety of Ivermectin Lotion 0.5% (Actavis Laboratories UT, Inc.) to SKLICE® (ivermectin) Lotion, 0.5% (Arbor Pharmaceuticals, LLC) in the Treatment of Human Head Lice Infestation

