10.4 Treatments

10.4.1 Treatments Administration

Patients will be provided with verbal and written instructions on how to administer the study product at home. At Visit 1, eligible patients will receive a 4 oz (117 g) tube of randomized study product (i.e., Test, Reference or Placebo). Study product should be applied on the day of or the day after enrollment into the study. The day of dosing will be considered Day 1. Patients, infested household members, and/or caregivers will be instructed to apply the study product to dry hair in an amount sufficient (up to 1 tube) to thoroughly coat the hair and scalp, avoiding contact with the eyes. Study product should be left on the scalp for 10 minutes before rinsing with water only. Patients should wash their hands after application of the study product. Hair should be allowed to dry naturally (pat drying with decontaminated towel is permitted) and left uncovered after application of the study product. Following application and rinsing of the study product, patients may not shampoo, wash, or rinse their hair or scalp until the Day 2 visit has been completed.

If any non-infested household member is pregnant or lactating at the time of the study, this person may not be involved with application of the study product to any household members.

The study product should be applied as a single dose. Patients should not use the product more than once. Tubes of study product will be collected at Visit 2 and the site will verify the product was used and rinsed. If a patient inadvertently does not return a tube of study product at its respective return visit, the patient should be instructed to return it as soon as possible or at the next visit.

On Day 1, before applying treatment, all bedding, hats, clothing, and towels used by infested persons or their household, sexual, and close contacts in the two days before treatment should be decontaminated by machine washing in high temperatures (at least 150°F) and drying in a hot dryer for at least 20 minutes (additional time should be added if large loads are dried). Clothing or items that are not washable can be dry-cleaned or sealed in a plastic bag and stored for two weeks. Personal care items such as combs, brushes, and hair clips should be washed in hot water (at least 135°F) for 10 minutes. Instructions on good hygiene and proper methods of decontamination will be provided to the patient and caregivers.

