10.8 Early Termination (Patient, Study)

A patient may terminate from the study early for any reason at any time without any disadvantages. In this case, the Investigator should make every effort to have the patient return to the next scheduled visit to perform all required End of Study / Study Completion / Early Termination visit activities and to collect and reconcile all test articles. If the patient does not return for the End of Study / Study Completion / Early Termination visit, the site should fully document the reason for early termination. All data, including the date and primary reason for termination, must be recorded on the End of Study / Study Completion / Early Termination eCRF, and source document.

Any patient who experiences an AE may be terminated from the study or from study treatment at any time at the discretion of the Investigator. In this case, the patient should be followed at the discretion of the Investigator until the resolution or stabilization of the AE. All applicable data should be recorded in the AE section of the eCRF. If a patient terminates from the study early for multiple reasons that include AEs, the End of Study / Study Completion / Early Termination eCRF should indicate that early termination was related to an AE.

An exception to this requirement will be the occurrence of an AE that in the opinion of the Investigator is not severe enough to warrant early termination but that requires the use of a prohibited medication, thereby requiring discontinuation of the patient. In such a case, the reason for discontinuation would be need to take a prohibited medication, not the AE.

The Investigator must inform the clinical project physician/clinical leader/Principal Investigator as soon as possible of all patients who are being considered for early termination due to AEs. Additional reports must be provided when requested.

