11.3.2 Modified Intent-to-Treat (mITT) Population

The mITT population will include all randomized patients who meet all inclusion/exclusion criteria, apply the study product as instructed, and return for at least one post-baseline evaluation visit.

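### Patients may be removed for non-compliance after the single Day 1 application at the investigator's discretion, and nothing then secures a Day 15 ± 2 examination for the mITT analysis

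*Protocol*

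**What the plan says.** Treatment is a single event. Protocol 10.4.1 states: "The study product should be applied as a single dose".

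Two sections give discretion to remove patients afterwards. Protocol 10.3.3, after listing prohibited products and procedures, says: "Any patient who violates any of the listed restrictions may be dropped from continued participation in the study by the Investigators". Protocol 10.3.4 gives non-compliance as a possible reason for removal, with examples that include "failure to make scheduled study visits in a timely fashion". Neither section says when removal should or should not follow.

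Three sections deal with what happens next:

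- Protocol 10.3.4: "If a randomized patient terminates from the study early, all efforts will be made to complete the End of Study procedures". No day is attached.
- Protocol 10.8: the investigator should "make every effort to have the patient return to the next scheduled visit" for the termination activities.
- Protocol 12.2.4: the Visit 4 form is completed for early terminators, whatever the day.

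The primary endpoint is the index patient's louse status at Day 15 ± 2 (Protocol 11.5). Membership of mITT requires eligibility, application as instructed, and that the patient "return for at least one post-baseline evaluation visit" (Protocol 11.3.2; SAP section 6 agrees). A later restriction breach or a late visit does not take a patient out of mITT.

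**The concern.** Once the only application has been made and rinsed off, removing a patient withdraws no study treatment. It can only end the collection of efficacy and safety data. Removal is not needed to keep PP clean either, because that definition already excludes significant protocol deviations. The superiority test, however, still needs an outcome for each of these patients.

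The plan therefore allows some Day 15 values to be missing by the site's choice rather than by the patient's refusal. Two patients with the same breach may end up with an observed Day 15 result at one site and a substituted one at another. The site has seen the louse examinations by then, so the choice need not be independent of outcome. Adverse event follow-up to Day 15 is shortened in the same way.

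**Working it through.** **Step 1: which examination results from removal.** The visits are Day 2, Day 8 ± 2 and Day 15 ± 2. Applying the 10.8 instruction:

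- Removed before Visit 2: next visit is Day 2.
- Removed after Visit 2 and before Visit 3: next visit is Day 6 to 10.
- Removed at Visit 3 or later: next visit is Day 13 to 17, so the endpoint is still observed.

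The gap under 10.8 is therefore confined to removals before Visit 3. Section 10.8 is also worded around termination by the patient. If it does not cover removal by the investigator, only 10.3.4 applies, and that sets no day at all. On either reading nothing requires a Day 15 ± 2 examination. An early examination may also be hard to tell apart in the data: early terminators have the Visit 4 form completed, and SAP listing L16.2.5 has one column for Visit 4 or discontinuation.

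**Step 2: whether an earlier examination can stand in.** SAP table T16.1.9.17 counts patients who are lice-free at Visit 2 and fail at Visit 3 or 4. The plan itself expects status to change before Day 15.

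**Step 3: who is affected.**

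- Patients not dosed as instructed are already outside mITT.
- Patients with live lice at Visit 2 or 3 are to be discontinued under 10.6.7 in any case, and they are observed failures.
- What remains is mainly patients who were lice-free when last examined.

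**Step 4: size (illustration only).** The planning rates, power, allocation ratio and dropout allowance are blacked out, so the 378 index patients in the protocol cannot be reproduced. The figure is used only for scale. The SAP's 364 rests on protocol Rev. 0.

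Assumptions:

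- Allocation 1:1:1, so 378 / 3 = 126 per arm.
- A share d of each arm is removed while lice-free and has no Day 15 examination.
- 85% of those removed on active (qA) and 50% on placebo (qP) would have been Day 15 successes.

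With true rate p, the arm's analysed rate is p − d·q if the missing values count as failures, and p + d·(1 − q) under LOCF. Under either rule the active-placebo difference is

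(pA − pP) − d·(qA − qP) = (pA − pP) − 0.35d.

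For pA = 65%, pP = 40%, d = 10% (12.6 patients per arm):

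- Failure rule: 0.65 − 0.085 = 0.565 and 0.40 − 0.05 = 0.35, difference 0.215.
- LOCF: 0.65 + 0.015 = 0.665 and 0.40 + 0.05 = 0.45, difference 0.215.

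Power, two-sided 5%, unstratified normal approximation:

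Φ{[Δ − 1.96·√(2p̄(1 − p̄)/n)] / √([pA(1 − pA) + pP(1 − pP)]/n)}.

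| d | Patients per arm | Difference (points) | Power, 1:1:1 |
|---|---|---|---|
| 0 | 0 | 25 | 98% |
| 5% | 6.3 | 23.25 | 96% |
| 10% | 12.6 | 21.5 | 93% |
| 20% | 25.2 | 18 | 83–84% |

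If allocation were 2:2:1 (about 151, 151 and 76), power would be 95% at d = 0, 87–88% at d = 10% and 75% at d = 20%. With true rates of 75% and 20%, power stays above 99% throughout.

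**The case against.** A reader might infer that the Day 15 outcome is simply lost at the site's discretion. The documents do not support that. Sections 10.3.4, 10.8 and 12.2.4 all call for closing procedures or a Visit 4 record, and a missing value in mITT is imputed. What stands is that the examination has no required day.

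A reader might also infer that late attendance at Visit 3 costs the endpoint. Under 10.8 that patient's next visit is Visit 4. Late attendance is, moreover, a ground under 10.3.4 and not under 10.3.3.

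A third inference is that sites could steer the comparison. Investigators and site staff are blinded (10.4.5), the test is stratified by site, and patients with live lice at Visits 2 and 3 are to be discontinued anyway. Different removal habits between sites do not by themselves favour an arm. In the illustration, with equal removal across arms, the difference shrinks, which works against the superiority claim.

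Fourth, one could quote a swing in an arm's success rate equal to the removed share: 10 points for 10% removed, if all were lice-free and are counted as successes under one rule and failures under the other. That swing measures a different defect. Protocol 11.6, the synopsis and SAP 8.2.1 specify LOCF, while another synopsis sentence counts missing Day 15 data as failure. Reconciling the two removes the swing. It would not restore the observation, which is the point made here.

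Finally, the remedy reaches few patients. Three of the four bulleted restrictions in 10.3.3 concern other lice or anti-parasitic treatment, and after such use a Day 15 result no longer reflects study product alone. This objection stands, and it limits the gain.

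**Conclusion.** The point holds in limited form. Removal for non-compliance is discretionary, has no criteria, and comes after the only dose. For a patient removed before Visit 3, the Day 15 ± 2 observation in mITT may be replaced by an earlier examination or an imputed value.

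The effect falls on the superiority analysis and on safety follow-up. It does not extend to PP equivalence as far as the legible PP criteria show; part of that definition is blacked out.

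The size rests on a removal rate that the documents do not give, and it is probably small. In the weaker assumed scenario (65% against 40%), 10% removed costs 3.5 points of difference and about 5 points of power; in the stronger one (75% against 20%), power is hardly affected. These figures also assume equal removal in all arms and the stated 85% and 50%. This is a cheap improvement, not a threat to the trial's conclusions.

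**What to change.** In Protocol 10.3.3, 10.3.4 and 10.8, state that non-compliance is recorded as a deviation that may exclude the patient from PP but does not by itself end follow-up. Unless consent is withdrawn, or the patient is withdrawn for safety or under the existing live-lice provisions, the Visit 4 (Day 15 ± 2) louse examination and adverse event review are still done.

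In Protocol 11.6 and SAP 8.2.1, use that observed result in mITT where no other lice treatment was used. Patients who did use other lice treatment follow the single missing-data rule that emerges once LOCF and the failure rule have been reconciled.

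While editing 10.8, also reconcile its sentence that treats an adverse event needing a prohibited medication as requiring discontinuation with the permissive wording of 10.3.3.

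The cost is a short amendment, matching SAP text, and a few visits for patients who will not count in PP. Visit 4 is already scheduled for every patient.
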